Part 2 is an open-label, long-term safety study of ZX008 for subjects who have successfully completed 14 weeks of treatment (titration + maintenance) in Part 1 and are candidates for continuous treatment for an extended period of time; subjects who have not completed the entire 14 weeks of treatment in Part 1 may be eligible to participate in Part 2 on a case-by-case basis and only following sponsor approval. Part 2

Version 2.0

Syneos Health #1009529A

consists of a 12-month Open-Label Extension (OLE) Treatment Period and a 2-week Post-Dosing Period. Thus, subjects who were randomized to ZX008 during Part 1 and complete Part 2 will have been treated with ZX0008 for at least 70 weeks (including their participation in both Part 1 and Part 2).

During Part 2 all subjects are treated initially with 0.2 mg/kg/day for 1 month to assess effectiveness of this dose in all study subjects. After 1 month at a dose of 0.2 mg/kg/day, the investigator may adjust the dose for each subject based on effectiveness and tolerability. Dose changes should be made in increments of 0.2 mg/kg/day, to a maximum of 0.8 mg/kg/day (or 0.5 mg/kg/day for subjects taking concomitant STP) but not to exceed total dose of 30 mg/day (or 20mg/kg/day for subjects taking concomitant STP). During the 12-month OLE subjects will have ECG and ECHO assessments at months 1, 3, 6, and 9, and at the end of study visit.

A follow-up ECG and ECHO will be performed at 3 and 6 months after study drug discontinuation for early termination and for those subjects who complete Part 2. Subjects enrolled in Germany, France and Netherlands will have an additional follow-up at 24 months. If there are any findings at a post-dose follow-up, another follow-up will scheduled every 3 months until resolved or stabilized. In both Part 1 and Part 2 parents/caregivers will use a diary every day to record the number of seizures, type of seizures, time and duration of seizures, whether the seizure resulted in a drop, dosing of study drug, and use of rescue medication.

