4.4. ADMINISTRATION OF STUDY MEDICATION

Each bottle of study medication contains the appropriate concentration and volume of liquid to administer the assigned treatment (ZX008 0.2 mg/kg/day, ZX008 0.8 mg/kg/day [or 0.5 mg/kg/day for subjects taking concomitant STP], or placebo). ZX008 and placebo are identical, thus rendering the study drug and placebo indistinguishable.

The blinding scheme instituted for this study ensures that the volume of study medication taken cannot be associated with the dose group, thus unblinding the study. This is achieved by random assignment of different concentrations of ZX008 or placebo (1.25 mg/mL, 2.5 mg/mL, and/or 5 mg/mL) by the IWR system. The IWR system instructs site personnel to the volume of oral solution to be administered based on that subject's weight. (Dose is recalculated by the system based on weight once at the midpoint of Part 1 of the study.) During the Titration, Maintenance, and Taper/Transition Periods, the subjects and study personnel (investigators, clinical staff, personnel involved in data collection and analysis, the Medical Monitor, and the sponsor) are blinded to the treatment allocation and to the concentration of ZX008. If an investigator feels the blind should be broken, he/she can do so when necessary for treatment decisions. However, the investigator should endeavor to discuss with the Medical Monitor or Sponsor's Medical Representative, if available. The blind should only be broken in the event the knowledge of whether the subject is on active study medication versus placebo is needed to determine course of medical treatment for the event. The subject will be discontinued from the clinical trial upon breaking of the blind

and the decision whether the subject can enter Part 2 will rest with the Sponsor if the subject exited Part 1 prior to completion. Following randomization subjects enter the Titration Period and are blindly titrated to					
Following randomization their randomized dose	-	itration Period and are	blindly titrated to		
Table 1: Titration Algo	orithm for Part 1				
Randomized Group	Titration Step 1	Titration Step 2	Titration Step 3		
	Study Days 1-4	Study Days 5-8	Study Days 9-14		
ZX008 0.2	ZX008 0.2	ZX008 0.2	ZX008 0.2		
mg/kg/day	mg/kg/day	mg/kg/day	mg/kg/day		
ZX008 0.8	ZX008 0.2	ZX008 0.4	ZX008 0.8		
mg/kg/day (0.5	mg/kg/day	mg/kg/day	mg/kg/day		
mg/kg/day for			(0.5 mg/kg/day for		
subjects taking		(subjects		
concomitant STP)		1	taking concomitant		
		100	STP)		

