Placebo	Placebo	Placebo	Placebo		

After completion of the Titration Period, subjects enter the Maintenance Period and continue to receive the randomized dose of ZX008 or placebo and be treated for an additional 12 weeks.

Subjects who complete the Maintenance Period and do not be continue into Part 2, the open-label extension, and subjects who discontinue from Part 1 early, will be tapered off of study medication as outlined in Table 2.

Table 2: Taper Algorithm for Part 1

Randomized Group	Taper Step 1	Taper Step 2
\C	Day 1-4 after study	Days 5-8 after study
X Y	completion or early	completion or early
-0~	termination	termination
ZX008 0.2 mg/kg/day	Placebo	Placebo
ZX008 0.8 mg/kg/day (0.5	ZX008 0.4 mg/kg/day	ZX008 0.2 mg/kg/day
mg/kg/day for subjects		
taking concomitant STP)		
Placebo	Placebo	Placebo

Subjects who complete the Maintenance Period and will be continuing into the openlabel extension (Part 2) will be transitioned from double-blind study medication to open-label ZX008. All subjects entering the open-label extension (Part 2) will be transitioned from their blinded daily dose to the 0.2 mg/kg/day dose during the 2-week interval between Visits 12 and 15, without breaking the blind. The IWR system will assign two bottles of Investigational Medicinal Product (IMP) to the subject, one for

Version 2.0

Syneos Health #1009529A

each step in the transition. A new bottle of IMP will be started by the subject at each level of the transition step.

Table 3: Transition Algorithm for Part 1

	Tuble 3. Translation Algorithm		
	Dose Group in Double-	Transition Step 1	Transition Step 2
	Plind Ctudy	Day 1 4 after Visit 12	Day 5 14 after Visit 12
	ZX008 0.2 mg/kg/day	ZX008 0.2 mg/kg/day	ZX008 0.2 mg/kg/day
	ZX008 0.8 mg/kg/day (0.5	ZX008 0.4 mg/kg/day	ZX008 0.2 mg/kg/day
	mg/kg/day for subjects		
	Placebo	7Y008 0.2 mg/kg/day	7Y008 0. 2 mg/kg/day/
	1 tacebo	ZX000 0.2 mg/ kg/ day	Z/000 0.2 mg/kg/day
Kilis	The full list and timing of students of the full list and timing of the full list and time time full list and time full lis	ZX008 0.2 mg/kg/day ZX008 0.2 mg/kg/day ZX008 0.2 mg/kg/day dy procedures is provided in Tab	ole 4.
,	This documer 03.007A.03	nt is proprietary and confidential to Syr Syneos Health	neos Health Page 19 of 110

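### Table 2 sets the taper by randomised group alone, so for 0.8 mg/kg/day subjects who stop in Study Days 1-8 the first taper dose is above or equal to the Table 1 dose they were on

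*SAP*

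**What the plan says.** Section 4.4, Table 1, titrates the 0.8 mg/kg/day group in three steps. Read across, the row is "ZX008 0.8 ZX008 0.2 ZX008 0.4 ZX008 0.8" mg/kg/day for Study Days 1-4, 5-8 and 9-14, with 0.5 replacing 0.8 for subjects on STP.

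Table 2 gives the taper. It applies to completers who do not continue into Part 2, and the SAP adds that "subjects who discontinue from Part 1 early, will be tapered off of study medication as outlined in Table 2". Rows are randomised groups and columns are days after completion or early termination. The high-dose row reads "ZX008 0.8 mg/kg/day (0.5 ZX008 0.4 mg/kg/day ZX008 0.2 mg/kg/day" and the low-dose row reads "ZX008 0.2 mg/kg/day Placebo Placebo". Nothing in the table or its lead-in depends on the dose reached.

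Table 3 governs entry to Part 2: "All subjects entering the open-label extension (Part 2) will be transitioned from their blinded daily dose to the 0.2 mg/kg/day dose". Section 4 says that subjects who did not complete 14 weeks "may be eligible to participate in Part 2 on a case-by-case basis and only following sponsor approval".

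On routing, section 4 states that at the end of Maintenance or at early discontinuation a subject goes to taper or transition according to whether they leave the study or enrol in Part 2. The Taper/Transition row of section 6.7 and footnote h of Table 4 follow the same rule. Footnote b of Table 4, like the sentence above Table 2, sends all early discontinuers to taper.

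Section 6.7 also foresees that a taper may be omitted after early discontinuation, without saying when or by whose decision.

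**The concern.** A taper is meant to bring a subject off the drug. Because Table 2 ignores the titration step reached, a high-dose subject who leaves in the first days of treatment, possibly for intolerance, is assigned a first taper dose that is not below the dose being stopped. Section 4.4 keeps subjects, site staff, the Medical Monitor and the sponsor blinded to allocation and concentration through the taper, so the step would not ordinarily be visible at the site.

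For the analysis, what matters is how events after such a stop are labelled by period. Section 9.3 puts events after Visit 12 in Transition/Taper, and section 6.7 makes the early termination visit Visit 12. An event on an unchanged or higher dose could then be read as arising during withdrawal. Another rule in section 6.7 pulls the other way: for a subject who withdraws before Maintenance treatment, safety events up to and including the date of study withdrawal are tabulated in Titration. The SAP does not say whether that date is the early termination visit or the end of the taper.

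**Working it through.** **Inputs.** Doses from Tables 1, 2 and 3 (section 4.4); caps of 30 mg/day, or 20 mg/day with STP (section 4.3); 79 subjects per group and a 20% dropout allowance before Maintenance (section 4.2).

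**Step 1: dose ratio, 0.8 mg/kg/day group.** Ratio = Taper Step 1 dose / Table 1 dose at stopping.

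| Stop in Study Days | Dose at stopping (mg/kg/day) | Taper Step 1 (mg/kg/day) | Ratio |
|---|---|---|---|
| 1-4 | 0.2 | 0.4 | 2.0 |
| 5-8 | 0.4 | 0.4 | 1.0 |
| 9-14 | 0.8 | 0.4 | 0.5 |
| 9-14 with STP | 0.5 | 0.4 | 0.8 |

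Only stops from Day 9 onward give a step down.

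**Step 2: effect of the caps.** The SAP does not say whether the caps apply at each titration and taper step; assume that they do. For weight w and a stop in Days 1-4, ratio = min(0.4w, cap) / min(0.2w, cap).

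- Without STP, the cap first binds at 30/0.4 = 75 kg. At 75 kg: 30/15 = 2.0. At 100 kg: 30/20 = 1.5.
- With STP, it first binds at 20/0.4 = 50 kg. At 50 kg: 20/10 = 2.0. At 75 kg: 20/15 = 1.33. At 100 kg: 20/20 = 1.0.
- For stops in Days 5-8 the ratio is 1.0 at every weight.

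**Step 3: how many subjects.** The SAP gives no withdrawal pattern. Assume dropouts before Maintenance fall evenly over the 14 titration days, so that 4/14 fall in Days 1-4 and 4/14 in Days 5-8. Count per window = 79 x dropout rate x 4/14.

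- At 5% (assumed lower value): 79 x 0.05 = 3.95; x 4/14 = 1.1.
- At 20% (the SAP's allowance): 79 x 0.20 = 15.8; x 4/14 = 4.5.

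**Step 4: Table 2 against Table 3, Steps 1 and 2.**

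| Group | Table 2 (taper) | Table 3 (transition) | Doses |
|---|---|---|---|
| Placebo | placebo, placebo | 0.2, 0.2 | differ |
| 0.2 mg/kg/day | placebo, placebo | 0.2, 0.2 | differ |
| 0.8 mg/kg/day | 0.4, 0.2 | 0.4, 0.2 | same |

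For the 0.8 group only the length of Step 2 differs (Days 5-8 against Days 5-14).

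**The case against.** The strongest objection is that this is a brief description in an SAP. Dosing exceptions and IWR rules usually sit in the protocol, which is not shown, and editing the SAP changes no dispensed dose. That limits what can be claimed about doses actually given. It does not remove the conflict: the SAP restates the algorithm, extends it expressly to early termination and gives no exception.

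A second objection is that section 6.7 recognises that a taper may not take place, and section 4.4 lets the investigator break the blind when treatment decisions require it. Both are true. Neither says what happens to someone who stops in Days 1-8, and an omission rule with no trigger does not reconcile the tables. Together with the caps, though, it means one cannot say that every high-dose subject stopping in Days 1-4 has the dose doubled.

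A reader might also infer that early leavers who enter Part 2 fall under two tables that cannot both be followed. The document as a whole does not support that. Section 4, the Taper/Transition row of section 6.7 and footnote h of Table 4 all route by Part 2 entry. What remains is loose wording above Table 2 and in footnote b, which if followed would change doses only for the 0.2 mg/kg/day and placebo groups.

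Finally, a reader might conclude that post-stop events are certain to be tabulated as taper events. The Titration rule in section 6.7 makes that unclear. Full Part 1 adverse event tables by assigned group are unaffected, and the primary efficacy window ends at Visit 12 or early termination, before any taper dose.

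**Conclusion.** The point holds for the 0.8 mg/kg/day group. As written, Table 2 gives a first taper dose twice the Table 1 dose for stops in Study Days 1-4 and equal to it for stops in Days 5-8, against the table's stated purpose. The factor of two holds up to 75 kg (50 kg with STP) if the caps apply at each step, and is lower above those weights. It concerns the four days of Taper Step 1, where a taper is conducted.

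The number of subjects is unknown. The range of about 1 to 4-5 of 79 in each four-day window rests on even timing, which the SAP does not support, and its upper end uses a sample-size allowance rather than an expected withdrawal rate. The conflict is in the rule and does not depend on the count.

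Two lesser inconsistencies go with it: the taper-or-transition wording, and the boundary between the Titration rule in section 6.7 and the Taper rule in section 9.3.

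**What to change.** 1. Reconcile Tables 1 and 2 for subjects who stop in Study Days 1-8, and check the reconciled rule against the IWR configuration. This is for the sponsor to settle; the review does not say which dose or rule is right. State when a taper is not conducted.
2. Align the sentence above Table 2 and footnote b of Table 4 with the routing rule in section 4.
3. Reconcile section 6.7 with section 9.3, so that each event after a stop before Maintenance belongs to one defined period.
4. From dispensing records, flag any subject whose first taper dose equalled or exceeded the last titration dose, and list their taper-phase events by dose taken.

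The cost is wording alignment, a configuration check, one derived flag and one listing.

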5.3. ADDITIONAL SECONDARY EFFICACY ENDPOINTS

The additional secondary endpoints are:

ZX008 0.8 mg/kg/day and 0.2 mg/kg/day groups compared independently versus placebo on the

- Change from baseline during T+M in frequency of all seizures that (typically)
 result in drops (i.e., GTC, SGTC, TS, AS, TA) whether ESC confirmed as drop or
 not.
- Change from baseline during T+M in frequency of all countable motor seizures (GTC, SGTC, TS, AS, TA, CS, FS, and HS).
- Change from baseline during T+M in frequency of all countable non-motor seizures (absence, myoclonic, focal without clear observable motor signs, infantile spasms, and epileptic spasms).
- Change from baseline during T+M in the frequency of all countable seizures (i.e., motor and non-motor).
- Change from baseline during M in the frequency of seizures that result in drops.
- Change from baseline during M in the frequency of seizures that typically result in drops.
- Change from baseline during M in the frequency of all countable motor seizures.
- Change from baseline during M in the frequency of all countable non-motor seizures.
- Change from baseline during M in the frequency of all countable seizures (i.e., motor and non-motor).
- Proportion of subjects who achieve a worsening from baseline (i.e. ≤ 0% reduction), or >0%, ≥25%, ≥50%, ≥75%, or 100% reduction between baseline and T+M, and baseline and M, in seizures that result in drops (ESC confirmed), seizures that typically result in drops, all countable motor seizures, all countable non-motor seizures, and all countable seizures.
- Number of seizure-free days in the baseline, M and T+M period, defined as 1)
 days with no seizures that results in drops (ESC confirmed), and 2) days with no
 countable motor seizures
- The longest interval (days) between seizures that result in drops (ESC confirmed) comparing the ZX008 0.8 mg/kg/day and 0.2 mg/kg/day groups independently versus placebo

ALS

Laboratory safety (hematology, chemistry, urinalysis)

Vital signs (blood pressure, heart rate, temperature, and respiratory rate)

Body weight and BMI

Physical examination

Neurological examination

BRIEF to measure changes in cognition of the subject

Columbia Suicidality Severity Rating Scale (C-SSRS)

12-lead ECGs
Doppler ECHOs
Chest x-ray (for subjects enrolled in France and Nether

EEG (for subjects enrolled in Italy only)

EXPLORATORY FNET

5.4.

The safety endpoints for Part 1 of the study are:

5.5.

The exploratory endpoints for Part 1 of the study are:

- The change from baseline in behavior using the Vineland Adaptive Behavior Scale (VABS)
- The change from baseline in quality of life (QoL) using the Quality of Life in Childhood Epilepsy (QOLCE)
- The change from baseline in caregiver burden using the Zarit Caregiver Burden Inventory
- The change from baseline in affective symptoms of parent/caregiver using the HADS scale
- Incidence of status epilepticus in the M and T+M period.
- Incidence of rescue medication usage in the T+M and M periods
- Number of days rescue medication used in the T+M and M periods
- Incidence in use of medical services to treat seizures in the M and T+M periods

ANALYSIS SETS

Separate analysis data sets will be produced for Cohort A and Cohort B. Cohort A will include subjects from North America, Europe, and Australia; Cohort B will include subjects from Japan.

Syneos Health #1009529A

6.1. **ENROLLED POPULATION**

The enrolled population is defined as all subjects who signed the informed consent form. This population will be used for listings.

6.2. SAFETY (SAF) POPULATION

All Part 1 safety analyses will be performed on the SAF Population defined as all randomized subjects who receive at least one dose of ZX008 or placebo.

6.3. MODIFIED INTENT-TO-TREAT (MITT) POPULATION

Salthoril Ation The mITT Population is defined as all randomized subjects who receive at least one dose of ZX008 or placebo and for whom at least one week of diary data are available. Subjects will be analyzed according to the treatment group to which they were randomized. The primary comparison of ZX008 0.8 mg/kg/day to placebo, as well as key secondary analyses, will be performed on the mITT Population.

PER PROTOCOL (PP) POPULATION 6.4.

The PP Population is defined as all randomized subjects who receive at least one dose of ZX008 or placebo, who complete at least 4 weeks of diary data in the maintenance period, and who have no major protocol deviations that would have a significant impact on clinical outcome of Part 1 data, and who have met the inclusion criteria for baseline drop seizure count. Protocol deviations that occurred during Part 1 will be reviewed and the list of deviations warranting exclusion from the PP Population will be finalized prior to study unblinding.

PROTOCOL DEVIATIONS 6.5.

Major protocol deviations will be summarized overall and by site based on the SAF population. Major protocol deviations are those that have the potential to impact subject safety and/or affect data integrity and/or the efficacy conclusions. Major protocol deviations will be grouped into categories and may include categories such as:

- Violation of inclusion/exclusion criteria
- Violation of randomization inclusion criteria
- Non-compliance regarding intake of IMP
- Inappropriate intake of concomitant medication
- Subject not discontinued as per protocol
- Other non-compliance

Multiple deviations can occur in the same subject and thus a subject can be counted in more than 1 deviation category.

Major and minor protocol deviations will be presented in a subject data listing for the enrolled population, sorted by treatment, site, subject, and study part.

Deviations will be reviewed prior to the database lock of Part 1 data to determine which deviations will be classified as leading to exclusion from the PP set.

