4.2. DETERMINATION OF SAMPLE SIZE

The sample size for Part 1 Cohort A was estimated under the assumption that adding ZX008 at 0.8 mg/kg/day to current therapy will lead to a mean decrease in drop seizures that is 30 percentage points greater than adding placebo to current therapy. For example, if adding placebo leads to a 10% decrease in seizures, then adding the high dose of ZX008 would be expected to decrease seizures by at least 40%. The variability expected in the trial was estimated from a Phase 3 trial of clobazam for patients with Lennox-Gastaut syndrome (Ng 2011) leading to an assumption that the standard deviation (SD) is 50%. Other assumptions include an allowance for 20% dropouts between randomization and the start of the maintenance period. Under these assumptions, a sample size of 63 subjects per treatment group for a nonparametric analysis affords 90% power to detect a difference between the ZX008 0.8 mg/kg/day and placebo groups that is significant at the α =0.05 level. Assuming a 20% drop-out rate prior to the start of the maintenance period yields a requirement for an additional 14 subjects per group for a total of 79 subjects per treatment group for a nonparametric analysis. Similar calculations for the 0.2 mg/kg/day ZX008 group lead to a total required

sample size of 237. The number of subjects randomized into Part 1 Cohort A is estimated to be approximately 250 due to the long baseline period.

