8. EFFICACY

The analysis of the Part 1 primary and secondary efficacy parameters will be performed on the mITT population for Cohort A and B independently, except where noted.

The Part 1 primary efficacy endpoint and key secondary efficacy analyses will be repeated on the PP Population for Cohort A and B independently, in order to assess the impact of major protocol deviations on the key inference.

All primary and key secondary variables will be analyzed for data obtained for the T+M period, and will be repeated for data obtained during the M period only.

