Two different methods for imputation of missing values due to subject drop out will be incorporated into the analysis of the primary efficacy endpoint. When referring to frequency in the paragraphs below, it refers to the number of seizure events per 28 days.

S1: Worst value substituted: In this analysis, for a subject who drops out of treatment, if the drop seizure frequency during T+M is lower than the baseline value, the baseline value will be substituted for the subject from the point of withdrawal to the end of the planned duration of T+M. However, if the seizure frequency during T+M is higher than the baseline value, there will be no substitution. The DSF for the planned duration of T+M will then be computed as a weighted mean of the value before dropout, and the imputed value after dropout. The weights will be the proportion of planned duration of T+M before and after dropout. The statistical analysis (nonparametric ANCOVA) described at the start of section 8.2.2 will then be performed on the resulting dataset. Treatment comparisons will be based on the least squares means and standard errors obtained from the ANCOVA.

S2: Differential imputation method: In this analysis, subjects who dropout due to an adverse event, lack of compliance, loss to follow-up or subject choice will have their

convulsive seizure frequency for the remainder of the time during the planned T+M period replaced with the worse of the observed value or the baseline value as described for S1. However, for other withdrawal reasons (e.g., "lack of efficacy") their observed DSF during T+M will be imputed for the remainder of the time between dropout and end of planned T+M. The DSF for the planned duration of T+M will then be computed as a weighted mean of the value before dropout and the imputed value after dropout. The weights will be the proportion of time before and after dropout. The statistical analysis (nonparametric ANCOVA) described at the start of section 8.2.2 will then be performed on the resulting dataset. Treatment comparisons will be based on the least squares means and standard errors obtained from the ANCOVA.

Criteria for Establishing Efficacy

While several supportive and/or supplementary analyses are specified above, the main criterion for demonstrating efficacy will be the primary non-parametric analysis for the mITT population from Cohort A.

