Figure	14.2.1.5.1.1	Cumulative Response Curve for Percent of Subjects Experiencing Various % Reductions in Seizures Resulting in Drops (ESC Confirmed) during Part 1 (Cohort A - North America, Europe, Australia) - mITT Population	
Figure	14.2.1.5.1.2	Cumulative Response Curve for Percent of Subjects Experiencing Various % Reductions in Seizures Resulting in Drops (ESC Confirmed) during Part 1 (Cohort B - Japan) - mITT Population	
Table	14.2.1.6.1	Frequency of Seizures Resulting in Drops (ESC Confirmed) per 28 days during Part 1 by Age Subgroup: Nonparametric Analysis (Cohort A - North America, Europe, Australia) - mITT Population	
Table	14.2.1.6.2	Frequency of Seizures Resulting in Drops (ESC Confirmed) per 28 days during Part 1 by Sex: Nonparametric Analysis - (Cohort A - North America, Europe, Australia) mITT Population	
Table	14.2.1.6.3	Frequency of Seizures Resulting in Drops (ESC Confirmed) per 28 days during Part 1 by Weight Subgroup: Nonparametric Analysis - (Cohort A - North America, Europe, Australia) mITT Population	
Table	14.2.1.6.4	Frequency of Seizures Resulting in Drops (ESC Confirmed) per 28 days during Part 1 by Number of Concomitant Antiepileptic Medications Used:	

Versi	on 2.0	Syneos Health #1009529A	
		Nonparametric Analysis (Cohort A - North America, Europe, Australia) mITT Population	rilation.
Table	14.2.1.6.5	Frequency of Seizures Resulting in Drops (ESC Confirmed) per 28 days during Part 1 by Number of Prior Antiepileptic Medications Used: Nonparametric Analysis (Cohort A - North America, Europe, Australia) mITT Population	notilati
Table	14.2.1.6.6	Frequency of Seizures Resulting in Drops (ESC Confirmed) per 28 days during Part 1 by Baseline Frequency of Seizures that Result in Drops: Nonparametric Analysis (Cohort A - North America, Europe, Australia) - mITT Population	eo'i.
Table	14.2.1.7.1	Frequency of Seizures Resulting in Drops (ESC Confirmed) per 28 days during Part 1: Nonparametric Analysis - Sensitivity to Missing Data Analysis 1 (Worst Value Substituted for Dropouts) (Cohort A North America, Europe, Australia) - mITT Population	
Table	14.2.1.7.2	Frequency of Seizures Resulting in Drops (ESC Confirmed) per 28 days during Part 1: Nonparametric Analysis - Sensitivity to Missing Data Analysis 1 (Worst Value Substituted for Dropouts) (Cohort B - Japan) - mITT Population	

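### If the mITT diary week means post-dose diary, the dropout sensitivity analyses S1 and S2 leave out the earliest dropouts

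*SAP*

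**What the plan says.** SAP section 6.3 defines mITT as randomised subjects with at least one dose and "for whom at least one week of diary data are available", analysed as randomised. The primary comparison and "key secondary analyses, will be performed on the mITT Population". Section 8 makes mITT the default: analyses of "primary and secondary efficacy parameters will be performed on the mITT population for Cohort A and B independently, except where noted". The only other efficacy set is PP (section 6.4), restricted among other conditions to subjects "who complete at least 4 weeks of diary data in the maintenance period".

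Section 8.2.3 plans two analyses for dropout. In S1, for a subject whose T+M drop seizure frequency is below baseline, "the baseline value will be substituted for the subject from the point of withdrawal to the end of the planned duration of T+M"; a frequency above baseline is left as observed. S2 uses the same rule for withdrawal due to an adverse event, non-compliance, loss to follow-up or subject choice, and carries the observed frequency forward for other reasons.

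In the section 14 index, the S1 tables ("Sensitivity to Missing Data Analysis 1 (Worst Value Substituted for Dropouts", 14.2.1.7.1 and 14.2.1.7.2) and the S2 tables (14.2.1.7.3 and 14.2.1.7.4) are all on mITT. The 2021 addendum repeats the Cohort A S1 and S2 tables on revised seizure files, again on mITT.

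**The concern.** Whether a dosed subject reaches a week of post-dose diary depends on what happens after randomisation. S1 and S2 exist to test whether such withdrawals could change the conclusion. On a post-dose reading of section 6.3, the earliest withdrawals are removed before either method can act.

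S2 withholds the observed benefit from subjects who leave for an adverse event, non-compliance, loss to follow-up or their own choice. A subject who leaves for one of those reasons with under a week of diary gets no such treatment and simply drops out. The same subjects leave the denominators of the 50% responder and investigator CGI-I tests, both of which are in the testing hierarchy of section 8.1.

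If early loss were similar across arms, little would change. If it were heavier on active treatment, the mITT difference would be more favourable than one that counts those subjects, and the planned sensitivity analyses could not reveal it.

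**Working it through.** **Which subjects each analysis covers (post-dose reading)**

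- Primary and key secondary: mITT (sections 6.3 and 8), so subjects under one week are out.
- S1 and S2: mITT (section 14 index), out.
- PP repeats: at least 4 weeks of Maintenance diary (section 6.4), out.
- Disposition (7.1) and adverse events (9.3.1, on the set in 6.2): in.

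No efficacy analysis of all randomised or all dosed subjects is listed.

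**The plan's sample size (section 4.2)**

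Inputs: 30-point difference, SD 50, two-sided 5%, power 90%. A two-sample t-test needs 59.35 per group. Dividing by the Wilcoxon efficiency 3/π gives 62.15, so 63. With 20% dropout, 63/0.8 = 78.75, so 79, and 3 × 79 = 237. The plan's 63, 79 and 237 reproduce. The stated addition of 14 per group does not (79 − 63 = 16), but that is a separate slip. The mITT question does not change the required N.

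**How many could be affected**

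The only early-loss figure is "an allowance for 20% dropouts between randomization and the start of the maintenance period", a two-week span. Spread evenly (assumption), week 1 takes 20% × 7/14 = 10%, about 8 of 79 per arm. If all of it fell in week 1, it would be 20%, about 16 of 79. The true rate is not given.

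**What counting them would do**

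Take the plan's example decreases (40% active, 10% placebo), let a and p be the shares lost in week 1, and count those subjects as 0% change. The difference becomes 40(1 − a) − 10(1 − p). Power comes from a simulated Wilcoxon test with 79 per arm, normal changes with SD 50 and 4,000 replicates.

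| Loss, active / placebo | Difference, excluded | Difference, counted as 0% | Power, excluded | Power, counted |
|---|---|---|---|---|
| 2% / 2% | 30 | 39.2 − 9.8 = 29.4 | 95.2% | 94.5% |
| 5% / 5% | 30 | 38 − 9.5 = 28.5 | 94.0% | 94.9% |
| 10% / 10% | 30 | 36 − 9 = 27 | 93.4% | 92.4% |
| 10% / 0% | 30 | 36 − 10 = 26 | 94.7% | 87.8% |
| 20% / 0% | 30 | 32 − 10 = 22 | 92.7% | 72.1% |

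The simulated mean differences agree with the formula to within about 0.3 points. Only unequal loss has a material effect on power.

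**Can S1 handle such subjects?**

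Yes. S1 is a time-weighted mean over the planned 14 weeks (98 days). A subject with 3 T+M diary days below baseline would be weighted 3/98 observed and 95/98 baseline.

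**The case against.** Several points against a stronger reading stand.

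- A reader might infer that no planned analysis counts these subjects. That is not so. Section 7.1 tabulates disposition and reasons by arm, the safety set keeps every dosed subject, and the index has a study populations table (14.1.1.3.1) and an allocation listing (16.2.3.2.1). The gap is in efficacy only.
- The exclusion depends on a reading. Section 6.3 does not tie the week to the post-dose period, and randomised subjects have about four weeks of baseline diary. Read literally, the criterion excludes almost nobody. That reading has its own problem: a subject with one T+M day enters the primary analysis at 28 times that day's count, and one with none still drops out because the denominator in section 8.2.1 is zero.
- Stopping in week 1 is not the same as having under a week of diary. Table 2 sets out an 8-day taper after early termination, and footnote h of Table 4 has a diary dispensed for it. If that diary counts, some early leavers would qualify.
- A reader might call these subjects treatment failures. The SAP does not show that, and under Table 1 nobody has reached 0.8 mg/kg/day in week 1.
- A minimum-data rule is defensible for a rate scaled to 28 days, which is a reason to leave the primary analysis on mITT.
- The active-only loss scenarios have no support in the SAP beyond the fact that only the 0.8 arm escalates, from Study Day 5.

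None of this gives S1 or S2 a way to include the earliest dropouts if the week is post-dose diary.

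**Conclusion.** The point holds conditionally. On the natural reading, that the week is post-dose diary, no planned efficacy analysis includes dosed subjects below that threshold, and S1 and S2 cannot show their effect. On the literal reading, the criterion is nearly empty and the wording still needs repair.

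The size is unknown. The scenario figures rest on an assumed week-1 loss, on 0% change for leavers (a convention, not a fact), and on means, whereas the primary test is a rank ANCOVA. They illustrate scale and are not an estimate of bias. A reader might take them to mean that the primary result is overstated by a fixed percentage; the SAP does not support that. With small or equal loss the effect is minor, and it becomes material only if loss is clearly heavier on active treatment.

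The primary analysis can stand. This is an inexpensive improvement to the two analyses meant to test dropout.

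**What to change.** 1. In section 6.3, state that the week refers to T+M diary.
2. Keep the primary analysis on mITT.
3. Run S1 and S2 (Tables 14.2.1.7.1 to 14.2.1.7.4) on all randomised subjects who took at least one dose, in their randomised arm. Apply each method's existing rule to subjects with some T+M diary. For those with none, set DSF_T+M equal to DSF_B, that is, 0% change.

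The cost is a wording change and a few more subjects in tables already planned. Rates based on a few diary days are noisy, although ranking limits their influence. The sensitivity estimate may come out somewhat less favourable. Sample size and the testing hierarchy are unaffected.
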